## 6.1 Schedule of Evaluations

CRESCENT Timeline	Project Month											
	1	2	3	4	5	6	7	8	9	10	11	12
Execute subcontract												
IMPACT IRB approval												
Select and randomize iCMP Nurse Care Managers												
Identify PWD and caregivers among selected iCMP Nurse Care Managers												
Adapt Care Ecosystem training for iCMP nurse care managers												
Provide adapted Care Ecosystem training to Nurse Care Managers												
Conduct Initial Survey of PWD and Caregivers												
Semi-structured interview of nurse care managers												
Conduct follow-up Survey of PWD and Caregivers												
Construct clinical and claims based study variables												
Analyze data, Summarize Findings												
Disseminate findings internally												
Disseminate findings externally												

## 6.2 Description of Evaluations

This section should include definitions of the row headings in the Schedule of Evaluations and any special instructions. All of the items listed on the Schedule of Evaluations should be described in this section.

### 6.2.1 Screening Evaluation

#### Consenting Procedure

Nurse care manager participation in the CareEco training is a quality improvement project and therefore consent is not applicable. Nurse care managers will be recruited to participate in individual phone-based semi-structured interviews by the study team. We seek a waiver of documentation of consent as interviews are low risk and will not be performed in person.

We will recruit caregivers of PWD to participate in a telephone interview. PWD will not be contacted within this study. We seek a waiver of documentation of consent as surveys of caregivers of PWD are low risk and will not be performed in person. We will review medical records of persons with dementia to identify their caregivers. Caregivers will be informed that their responses to these surveys will be kept entirely confidential. They will be given the option to opt out of answering the survey questions; those who opt out will not have their data included in the final analysis.

Finally, we will use existing Medicare Claims data and Epic medical record data to measure outcomes for PWD. Outcomes, by source, are listed in Table 1 above. We seek a waiver of informed consent for the use of these data. All data will remain on

secure drives within the health care delivery organization (as all study staff are part of the organization). The use of this secondary data is low risk and be presented in aggregate consistent with HIPPA protections when shared with members of the CRESCENT prime team.

### Screening

There will not be screening procedures for this study.

#### 6.2.2 Enrollment, Baseline, and/or Randomization

##### Enrollment

Patients who actively receive care management from the 30 identified nurses and who have a diagnosis of dementia within Medicare claims data will be identified as PWD for this study. We will leverage existing data within EPIC to identify caregivers for these PWD. Both PWD and their caregivers will be considered study subjects.

Preliminary examination of the structured fields within Epic that are used to house information on caregivers suggests that we will likely need to develop alternative methods, including review of notes, for identifying caregivers.

##### Baseline Assessments

**Caregiver survey:** Caregivers will be sent an advance letter about the study, and then calls to caregivers will occur at month three (prior to the launch of the CareEco intervention) and again at month nine. The survey battery administered during these calls will include:

- Caregiver Strain Index
- Caregiver Patient Health Questionnaire (PHQ-8)
- Neuropsychiatric Inventory Questionnaire (NPI-Q) (includes caregiver distress)
- Quality of Life in Alzheimer's Disease (QOL-AD) (includes caregiver and patient measures)
- Quick Dementia Rating Scale (patient)
- Experience of Care and Unmet Needs (adapted from CAHPS)

The surveys will be administered by phone in both English and Spanish to ensure responses from diverse patient and caregiver populations. Spanish versions will be administered by a trained, experienced bilingual interviewer with over four years of experience. Based on prior experience, we expect 50-60% of PWD caregivers will respond. We will assess the extent to which patients with less severe dementia would be able to self-report their symptoms, but for this pilot only caregivers will be surveyed.

**Nurse care manager interview:** A semi-structured interview of nurse care managers will be conducted at month five (two months following the launch of the adapted CareEco intervention) for quality assessment purposes. Interviews will be conducted by telephone at the convenience of the care manager and will last approximately 30 to

40 minutes. Interview domains will include 1) General experience in caring for PWDs and their caregivers; 2) Experience in direct outreach to caregivers and patients (including identifying the most knowledgeable or engaged caregivers); 3) Perceptions of services most needed and most difficult to arrange for patients with dementia and their caregivers; 4) Assessment of the adequacy of training as adapted to the iCMP context; and 5) Recommendations for further adaptation of the CareEco model. These data will be used to identify implementation barriers, and improve care quality.

#### Randomization

Nurse care managers selected by for participation in training will be randomly assigned to early vs. delayed training. Preliminary estimates based on 2018 data suggest that on average nurse care managers have 10 Medicare beneficiaries diagnosed with dementia on their panels, yielding approximately 300 PWDs and their caregivers overall; 150 receiving care management from nurses who receive early training, and 150 receiving care from nurses who receive delayed training. PWD and their caregivers will be blinded as to the timing of Adapted Care Ecosystem training of their iCMP care manager.

#### 6.2.3 Follow Up/Final Evaluation

Refer to “Baseline Assessments” for a description of the assessments that will be used to collect data from PWDs/caregivers at both baseline and follow-up.

**Medicare claims data** will be used to construct measures of health care utilization and costs. This data will be accessed in months eight and nine.

**Epic clinical data** will be used to capture PWD and caregiver outcomes documented in the iCMP note and to identify whether medication reconciliation and serious illness conversations/advance care planning occurred related to the iCMP interaction. In addition, Epic elements flow to tables within the Partners data warehouse.

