### Interventions and Duration

The adapted Care Ecosystem intervention will include three distinct phases:

- (1) Developing an adaptation of Care Ecosystem training and workflows through feedback from a workgroup consisting of recently retired highly experienced iCMP nurse care managers, an iCMP medical director, a dementia expert, pharmacist, and an active caregiver.
- (2) Training of iCMP nurse care managers in the adapted version of Care Ecosystem (e-learning modules and workflows, 1-day in-person training).
- (3) Implementing the adapted Care Ecosystem intervention with trained nurse care managers.
- (4) Booster sessions and process audits to augment intervention fidelity

We will compare the outcomes detailed above between the early training nurse cohort and the delayed training nurse cohort.

We plan to spend the first 3 months of the project collecting feedback and adapting the training. Nurse care managers will be trained at the end of month three. Outcome measures will be collected at the end of month nine. The delayed training cohort will receive training in month ten.

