- We anticipate that nurses who receive training will change the way they provide care to all their patients with dementia. However, measurement of patient-level process and outcome measures will be among patients who have an indication of dementia within their Medicare claims data and who are actively engaged with care management as of the date care managers in the early training cohort are trained. Preliminary estimates based on 2018 data suggest that on average nurse care managers have 10 Medicare beneficiaries diagnosed with dementia on their panels, yielding approximately 300 PWDs and their caregivers (150 patients in each arm).
- We will spend the first 3 months of the project collecting feedback and adapting the training. The nurse care managers who are assigned to receive

early training will be trained at the end of month three, while those assigned to receive delayed training will be trained at the end of month 9.

- Adapted Care Ecosystem training for the nurse care managers will occur via video-based learning as well as a 1-day in-person training held at the Assembly Row headquarters of Partners HealthCare.
- Study subjects include patients receiving care from 30 nurse care managers serving primary care practices with the highest proportions of minority / low SES patients. Nurse care managers will be randomly assigned to early vs. late training. Preliminary estimates based on 2018 data suggest that on average nurse care managers have 10 Medicare beneficiaries diagnosed with dementia on their panels, yielding approximately 300 PWDs and their caregivers overall; 150 receiving care management from nurses who receive early training, and 150 receiving care from nurses who receive delayed training. PWD and their caregivers will be blinded as to the timing of Adapted Care Ecosystem training of their iCMP care manager.
- All measurement and analysis will be performed by the study team using data housed within an existing Partners IRB approved Population Health Data Repository, or new quality improvement data collected by members of the study team.

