- (2) **Training iCMP nurse care managers in the adapted version of CareEco.** Prior to the 1-day in-person training, the care managers will engage in approximately 60 minutes of e-learning of the abbreviated video training. The virtual training through video technology (secure Zoom platform) will occur all in one day and will address communication skills, the use of the CareEco protocols, documentation expectations and workflow concerns. For their involvement, iCMP care managers will receive a stipend and CEU credits. On a weekly basis, the intervention team will offer an hourly check-in to address any questions that arise. The iCMP nurse care managers will also have access to a dementia care expert, in addition to their pre-existing social work and pharmacy team. The intervention team will monitor for intervention fidelity and work with iCMP nurse care managers if deviation from the adapted assessment and protocols are observed. Nurses in the early training cohort will receive their training in month three or month four, while nurses in the delayed training cohort will receive their training at the beginning of month ten.
- (3) **Implementing the adapted CareEco intervention with trained nurse care managers.** The adapted CareEco model will be delivered by the iCMP nurse managers within Partners HealthCare to patients on their panels as clinically appropriate. All care to PWD and their caregivers will be delivered over the phone. The care managers will always address immediate needs first, then screen for common problems and provide personalized support and standardized education using the adapted CareEco Care Plan Protocols; Medications, Safety, Referrals and Caregiver Education, Caregiver Well-being, Behavior Management, and Advance Care Planning. Call frequency will be about monthly but personalized to each dyad's needs and preferences. The study team will offer booster sessions and coaching over the course of the study to iCMP nurse managers who either ask for assistance or who, through chart audits, do not appear to be integrating the training into the care of their PWD. Implementation will occur following completion of training for the nurse care managers randomized to the early training cohort.

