Interviews will be scheduled two months after the launch of the CareEco training (month five). These interviews will be conducted in care manager offices or by telephone or a video technology platform at the convenience of the care manager. The interviews will last approximately 30 to 40 minutes. Research with the iCMP care management staff, conducted by our team in both 2017 and 2018 as part of a PCORI funded study of care management programs, achieved 75% participation rates. Interview domains will include 1) general experience in caring for PWD and their caregivers; 2) experience in direct outreach to caregivers and patients (including identifying the most knowledgeable or engaged caregivers); 3) perceptions of services most needed and most difficult to arrange for patients with dementia and their caregivers; 4) assessment of the adequacy of training as adapted to the iCMP context; 5) recommendations for further adaptation of the CareEco model, and 6) among care managers not participating in the training, implementation

barriers, including contextual factors, fit and overarching issues that impacted non-participation.

The following table summarizes the measures that will be used in this study.

Variable	Source	Primary or secondary outcome	Description
ED visits	Medicare Claims data	Primary	ED visits per member per month over 6 months; Feasibility of collection (Primary objective), difference between early and delayed cohorts (secondary objective)
Service utilization and costs	Medicare Claims data	Secondary	Hospitalizations, Observation stays, urgent visits, total medical expense; Feasibility of collection (Primary objective), difference between early and delayed cohorts (secondary objective)
Documentation of advance care planning	Epic	Secondary	
Documentation of medication review and reconciliation	Epic	Secondary	
Caregiver Depression *	Caregiver survey	Primary and Secondary	PHQ-8 (8 item)
Caregiver strain and burden *	Epic	Primary and Secondary	Caregiver Strain Index presence in Epic and magnitude
Caregiver strain and burden *	Caregiver survey	Primary and Secondary	Zarit Rating Scale (12-item) 
Behavioral Symptoms of Dementia *	Epic and Caregiver survey	Primary and Secondary	NPI-Q (Neuropsychiatric inventory Questionnaire)  presence in Epic and magnitude
PWD quality of life	Caregiver survey	Secondary	QOL-AD (13 items) 

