2.2 Primary outcome measure

The primary outcome is the change in ED visits per member per month from the 12 months prior the adapted Care Ecosystem training to the 6 months post training.

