3 STUDY METHOD

This is a pragmatic randomized quality improvement pilot trial to assess the feasibility and effectiveness of an adapted Care Ecosystem dementia care training for pre-existing nurse care managers who provide care management to high-risk patients. 15 integrated care management program (iCMP) nurse care managers were randomly assigned to receive early Care Ecosystem training (intervention) and the remaining 15 assigned to received Care Ecosystem delayed training after the study period (control). The time period of interest for outcomes in intervention and control groups is the 6-month period between early and delayed training.

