8 STATISTICAL ANALYSES

8.1 Primary outcome analysis

The change in ED visits PMPM from 12 months prior to training to 6 months post-training for intervention and control cohorts are compared using a differences-in-differences model with a negative binomial distribution (to account for utilization count data) and log link. This model estimates a difference-in-differences rate ratio that provides an estimate of the relative rate reduction/increase in ED visits PMPM in the intervention group as compared to controls.

Models included a weight for the number of member months in the pre and post periods, allowing PWD with more member months (and therefore more stable estimates) to contribute more strongly to the intervention effect. The training (“enrollment”) month was not included in either pre or post period. Models adjusted for baseline utilization and demographic characteristics (race, ethnicity, age) that differed across intervention and control cohorts. A sensitivity analysis removed PWD who died in the post period.

We hypothesized high feasibility in measuring ED visits for this population but had no specific hypothesis regarding whether the program would impact ED utilization in the relatively short 6 month-post period.

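### Claims access is scheduled for months 8 and 9, no later than the close of the six-month ED window and with no run-out, so the primary outcome would be cut short on almost any reading of the calendar

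*Protocol*

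**What the plan says.** **Access date.** Protocol 6.2.3 says of the Medicare claims: "This data will be accessed in months eight and nine". The Précis, under Interventions and Duration, puts collection of outcome measures at the end of month nine.

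**Early training.** The Précis says "Nurse care managers will be trained at the end of month three", and Protocol 3 agrees: those assigned to "early training will be trained at the end of month three". Protocol 5.1 is looser: "Nurses in the early training cohort will receive their training in month three or month four". Delayed training is at the end of month 9 (Protocol 3) or the beginning of month 10 (Protocol 5.1).

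**Outcome window.** The measures table in Protocol 6 sources the primary outcome to Medicare claims and defines it as "ED visits per member per month over 6 months". SAP 2.2 makes it a change "from the 12 months prior the adapted Care Ecosystem training to the 6 months post training". SAP 8.1 adds that the training "month was not included in either pre or post period". SAP 3 fixes the contrast: "The time period of interest for outcomes in intervention and control groups is the 6-month period between early and delayed training".

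**Completeness.** Protocol 9.3 expects little missing data because the records already sit in a repository. Neither document gives a claims lag, a run-out period, a paid-through date or a later refresh.

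**The concern.** The scheduled access ends no later than the outcome window it has to cover, and claims normally need some time to arrive. Followed as written, the 12-month pre-period would be mature while the last post-period months were partly or wholly empty.

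The SAP has no safeguard against this. SAP 7.1.1 admits a patient with at least one member month of fee-for-service eligibility and ACO alignment in each period, and SAP 8.1 weights by member months. Both concern eligibility, not whether the claims for a month have arrived. A month without its claims would count as observed, at full weight, with too few visits. SAP 7.3 rules out imputation.

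Two things are at stake. The primary objective is the feasibility of collecting ED data, so the timing and completeness of the extract are part of what is being tested. Protocol 9.2 also wants the pilot to inform effect sizes for a full-scale study, and an understated ED rate would carry into that design.

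**Working it through.** **Inputs.** Training at the end of month 3 (Précis; Protocol 3), or in month 4 (the later option in Protocol 5.1). Window of six months with the training month excluded (SAP 2.2, 8.1). Access in months 8 and 9 (Protocol 6.2.3). Claims lag: not given, so assumed at 0, 1, 2 and 3 months.

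**The plan's own figure.** From the end of month 3 to the end of month 9 is 9 − 3 = 6 months, which reproduces the six-month period between early and delayed training in SAP 3.

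**Window close.** Let t be the end of the training month. The window closes at t + 6:
- month-3 training: 3 + 6 = end of month 9 (window months 4 to 9)
- month-4 training: 4 + 6 = end of month 10 (window months 5 to 10)

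**Months covered.** k = min(6, pull date − lag − t). The start of month 8 is time 7, its end is 8, and the end of month 9 is 9.

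| Training | Pull | Lag 0 | Lag 1 | Lag 2 | Lag 3 |
|---|---|---|---|---|---|
| End of month 3 | start of month 8 | 4 | 3 | 2 | 1 |
| End of month 3 | end of month 8 | 5 | 4 | 3 | 2 |
| End of month 3 | end of month 9 | 6 | 5 | 4 | 3 |
| In month 4 | start of month 8 | 3 | 2 | 1 | 0 |
| In month 4 | end of month 8 | 4 | 3 | 2 | 1 |
| In month 4 | end of month 9 | 5 | 4 | 3 | 2 |

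One cell reaches 6: month-3 training, a pull on the last day of month 9, and no lag.

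**Effect on each arm's rate.** Suppose all six months are counted in the denominator but visits are seen for only k of them. At a constant rate, the post-period rate is understated by 1 − k/6: 17%, 33% or 50% for k = 5, 4 or 3. Partial arrival of claims would make this smaller.

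**Effect on the rate ratio.** If the same fraction c of visits is captured in both arms, the post-period ratio is (c × rate₁)/(c × rate₀) = rate₁/rate₀, so c cancels.

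**Effect on precision.** Take Poisson counts, equal rates, 12 complete pre-period months and k usable post-period months. The variance of the log difference-in-differences rate ratio is then proportional to 1/12 + 1/k. Relative to k = 6, the standard error ratio is √[(1/12 + 1/k)/(1/12 + 1/6)], where the denominator is 0.250:
- k = 5: √(0.283/0.250) = 1.06, up about 6%
- k = 4: √(0.333/0.250) = 1.15, up about 15%
- k = 3: √(0.417/0.250) = 1.29, up about 29%

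Overdispersion between patients would reduce these figures.

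**Earliest complete pull.** t + 6 + lag. For lags of 0, 1, 2 and 3 months this is the end of month 9, 10, 11 or 12 with month-3 training, and the end of month 10, 11, 12 or 13 with month-4 training.

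**The case against.** The strongest reply is that the Précis schedule works: training at the end of month 3, outcomes collected at the end of month 9, and a window that closes on that day. This stands as far as it goes. A reader might infer from 6.2.3 that the outcome can never be complete, and that is too strong, because the zero-lag pull on the last day of month 9 is a real exception. It is also the only one, and nothing in the documents supports zero lag.

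A reader might also infer that the analysed data were truncated. The documents do not show this. The SAP is written after the event, reports cohorts of 126 and 105, and describes a six-month post period without an extraction date. The claims sit in a standing warehouse, and 6.2.3 speaks of access, not of a final freeze, so a later pull is possible. The shading of the Section 6.1 timeline is not readable in the text available, so the months for building claims variables cannot be counted for or against the plan.

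A third inference is bias between the arms. Nurses were randomised, both arms share one calendar window, and nothing cited suggests that billing lag differs between them. That inference is not supported.

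A fourth is a larger loss of precision. Using the post period alone, √(6/k) gives 10%, 22% and 41% for k = 5, 4 and 3. The planned estimate also carries the variance of the 12-month pre-period, which truncation leaves unchanged, so 6%, 15% and 29% are the relevant figures.

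Finally, the month-4 case rests on Protocol 5.1 alone combined with the SAP's exclusion rule, and its window would run into delayed training. It is the weaker scenario, and it reflects an inconsistency in the training dates that needs resolving anyway. The main point holds without it.

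**Conclusion.** The point holds as a fault in the planned calendar. Access in months 8 and 9 falls no later than window close, no run-out is stated, and the SAP's member-month rule and weights would not correct the shortfall. With month-3 training and no lag, 4 to 6 of the 6 months are covered, depending on the day of the pull. With an assumed lag of 1 to 3 months and a pull at the end of month 9, 3 to 5 are covered.

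The consequence is an understated post-period ED rate in each arm, a pre-to-post change pulled downward in each arm, and a distorted reading of feasibility. The between-arm rate ratio would lose precision but is not shown to be biased. All sizes beyond the zero-lag row depend on a lag that the documents do not give, and the standard-error figures also depend on Poisson variance and equal rates. Because the rule as written would give incomplete data on the very outcome whose collection is being tested, it should be changed, not merely clarified.

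**What to change.** - Change Protocol 6.2.3 so that one frozen claims extract, the same for both arms, is taken after the post-training window closes plus a stated run-out. Size the run-out to the repository's actual lag.
- State the window in calendar dates, and report the extraction date and the paid-through date.
- Count only member months with complete run-out. If the extract has already been taken early, refresh it.
- Reconcile the training dates in the Précis, Protocol 3 and Protocol 5.1 so that the window ends before delayed training for every nurse.

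**Cost.** No new data collection, but a later claims analysis. A three-month run-out, taken as an example, reaches about month 12 of the 12-month timeline with month-3 training, leaving little room for analysis and dissemination. With month-4 training it reaches month 13, beyond the timeline. A shorter run-out would ease this if the repository's lag allows it.
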